3.4.4 Exclusion Criteria

Study candidates shall be excluded if they meet any of the following exclusion criteria:

Table 3.4.4-1 Exclusion Criteria	
Exclusion Criteria	
1.	Ocular disease, such as choroidal neovascularization, glaucoma and diabetic retinopathy, in either eye that may confound assessment of the retina morphologically and functionally.
2.	Intraocular surgery in the primary study eye within 90 days prior to baseline visit.
3.	Current or previous participation in an interventional study to treat STGD such as gene therapy or stem cell therapy. Current participation in a drug trial or previous participation in a drug trial within six months before enrollment. The use of oral supplements of vitamins and minerals are permitted although the use of Vitamin A supplementation shall be documented if available.
4.	The site Principal Investigator may declare any patient at their site ineligible to participate in the study for a sound medical reason prior to the patient's enrollment into the study.

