study procedures are summarized in Table 3.6.2 and graphically shown in Figure 5. In brief, if a patient is being screened for the prospective FFBCRI-PROGSTAR-02 study that visit can serve as the baseline visit for this retrospective (FFBCRI-PROGSTAR-01) study. If the patient participates in the prospective FFBCRI-PROGSTAR-02 study, the screening visit serves as “visit 1” of the prospective FFBCRI-PROGSTAR-02 study and simultaneously as the “visit -1” of the retrospective FFBCRI-PROGSTAR-01 study described herein if they have also been seen previously for at least 24 months, up to 60 months.

[figure not shown]

Figure 5: Overview to show the difference in possible datasets in the retrospective FFBCRI-PROGSTAR-01 Study, depending on number of available visits. 01 Study: the retrospective study. 02 Study: the prospective FFBCRI-PROGSTAR-02 Study.

Results will be sent by the participating centers to the Dana Center for Preventative Ophthalmology of the Wilmer Eye Institute, the Johns Hopkins University, Baltimore, for evaluation, with the exception of the microperimetry, autofluorescence and optical coherence tomography, which will be sent to a central reading center at the Doheny Eye

Institute, Los Angeles, California.

Primary outcome measure:

- Yearly rate of progression of STGD as reflected by the growth or the development of atrophic lesions measured by FAF imaging. Because patients have to have an atrophic lesion at the most recent visit, it is possible that they had no detectable lesion at earlier visits. Therefore, there are distinct scenarios as illustrated in Figure 6:

	Visit -3	Visit -2	Visit -1	Comment
Scenario 1	Atrophic Lesion: YES	Atrophic Lesion: YES	Atrophic Lesion: YES	2 Measurements of growth rate
Scenario 2	Atrophic Lesion: NO	Atrophic Lesion: YES	Atrophic Lesion: YES	1 Measurements of growth rate and secondary variables to study development of lesion
Scenario 3	Atrophic Lesion: NO	Atrophic Lesion: NO	Atrophic Lesion: YES	No Measurements of growth rate, but secondary variables to study development of lesion

Figure 6: Possible scenarios regarding the presence or the development of atrophic lesions as the primary outcome measure.

Secondary outcome measures:

- Yearly rate of progression of STGD as reflected by the rate of retinal thinning and photoreceptor loss as measured by sd-OCT.
- Yearly rate of loss of retinal sensitivity as measured by microperimetry.
- Yearly changes in best-corrected visual acuity.

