3.4.3 Inclusion Criteria

Study participants are required to meet the following inclusion criteria:

Table 3.4.3-1 Inclusion Criteria	
1.	Provide a signed informed consent/assent form and authorization allowing the disclosure and use of protected health information.
2.	The study eye must have at least one well-demarcated area of atrophy as imaged by fundus autofluorescence with a minimum diameter of 300 microns and the area of all lesions together must add to less than or equal to 12 mm ² (equivalent to no more than 5 disc areas in a least one eye) at the most recent visit.
3.	Two (2) or more pathogenic mutations confirmed present, in the ABCA4 gene. If only one ABCA4 allele contains pathogenic mutation(s), the patient shall have a typical Stargardt phenotype, namely at least one eye must have flecks at the level of the retinal pigment epithelium typical for STGD.
4.	Sufficient quality of imaging and psychophysical procedures in the opinion of the investigator.
5.	Patients have been followed for at least two (2) visits over a period of at least 24 months, up to 60 months, and had at least two examinations (same at all visits out of: Fundus Autofluorescence obtained with a Heidelberg Engineering instrument (e.g. HRA2, Spectralis); sd-OCT obtained with the Heidelberg Spectralis; Microperimetry obtained with the Nidek MP-1).
6.	Be at least six years old at the most recent visit (“visit -1”).
7.	Both eyes can be included if inclusion criteria are fulfilled for both eyes.

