3.7.2. Endpoints

3.7.2.1. Primary Statistical Endpoint

The primary endpoint is the rate of the growth or the development of atrophic lesions as measured by FAF imaging calculated over a period of at least 24 months, up to 60 months.

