4.2. Conflict of Interest

As this protocol does not support the development of a drug, device, or other intellectual property, there is no immediate concern about conflict of interest. If any concerns arise, conflict of interest statements will be obtained on a case-by-case basis.

5. Prohibited Medications

Study participants may use any systemic medications that are necessary. However, study participants should not participate or have participated in, or taken concomitant therapy, to treat Stargardt disease within six months before the observation period. Study candidates who have participated in an interventional study for Stargardt disease before the end of the retrospective observation period are also excluded – see study exclusion criteria.

6. Evaluation of Adverse Events

Not applicable.

7. Statistical Analysis

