Statistical Analysis Plan

ProgSTAR Study

FFBCRI-PROGSTAR-01	The Natural History of the Progression of Atrophy Secondary to Stargardt Disease: A Retrospective Longitudinal Observational Study
FFBCRI-PROGSTAR-02	The Natural History of the Progression of Atrophy Secondary to Stargardt Disease: A Prospective Longitudinal Observational Study
FFBCRI-PROGSTAR-02a	SMART Study: Scotopic Microperimetric Assessment of Rod Function in Stargardt Disease
Version	1.0
Date:	19 May 2018
Prepared for:	Foundation Fighting Blindness
Prepared by:	[name] and [name] Wilmer Eye Institute Johns Hopkins University

ProgStar Statistical Analysis Plan

Participant demographic and clinical characteristics at baseline (or the first ProgStar visit from the medical record review for the retrospective cohort) are first summarized. The progression rates of outcome measures from each testing modality (visual acuity from ETDRS test; mean sensitivity from microperimetry; decreased autofluorescence [AF] from fundus AF imaging; and retinal thickness and intact area from OCT) are estimated and reported separately. For each outcome, cross-sectional analysis using linear models with generalized estimating equations is first conducted for baseline data to understand factors associated with significantly different levels of baseline measurements. Longitudinal analysis is then conducted for each outcome to estimate its rate of progression and the associated risk factors. The data are longitudinally plotted over time to visualize the change during study period. A linear mixed-effects model (LMM) with a random intercept and a random coefficient for time is used to estimate the overall rate of change per year in the prospective and retrospective cohort, respectively. LMMs are also used to estimate the rates of change in subgroups stratified by the baseline level of the outcome. To further identify baseline variables associated with the rate of change, LMMs are used by including each baseline variable and its interaction with time. The univariate association of each variable with the change rate of the outcome variable is first estimated. Adjusted associations are also estimated using multivariable LMMs including variables either significantly associated with the change of outcome at p<0.1 or significantly associated with baseline outcome at p<0.1.

Additional statistical methods as appropriate for model construction are described in individual publications.

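### PROGSTAR-01's surgery and drug-trial exclusion windows are copied from the prospective study and leave most or all of its 24–60 month look-back uncovered

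*Protocol*

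**What the plan says.** All sections are in the PROGSTAR-01 protocol unless stated.

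- **3.4.4, criterion 2** excludes "Intraocular surgery in the primary study eye within 90 days prior to baseline visit". PROGSTAR-02 3.4.4 has the same sentence.
- **3.4.4, criterion 3** excludes "Current participation in a drug trial or previous participation in a drug trial within six months before enrollment", again as in PROGSTAR-02. The same criterion also excludes "Current or previous participation in an interventional study to treat STGD such as gene therapy or stem cell therapy", with no time limit.
- **3.7.2.1** defines the primary endpoint as a rate "calculated over a period of at least 24 months, up to 60 months". Inclusion criterion 5 in 3.4.3 requires that follow-up to exist already, with as few as two visits.
- **Section 3** says of a patient being screened for PROGSTAR-02 that "that visit can serve as the baseline visit for this retrospective (FFBCRI-PROGSTAR-01) study". If the patient joins PROGSTAR-02, it is also visit -1. Inclusion criterion 6, "Be at least six years old at the most recent visit", uses that label for the last visit of the look-back.
- **The SAP** summarizes characteristics at "baseline (or the first ProgStar visit from the medical record review for the retrospective cohort", which is the other end of the look-back.
- **Section 5** says participants should not have "taken concomitant therapy, to treat Stargardt disease within six months before the observation period". It separately excludes anyone who joined an interventional STGD study before the observation period ended, and refers the reader to the exclusion criteria.

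**The concern.** An exclusion window placed before baseline works in PROGSTAR-02 because the outcome data come afterwards. In PROGSTAR-01 the outcome data come first and enrollment follows. The time direction was reversed but the windows were not, so a window tied to enrollment, or to a baseline at the most recent visit, guards only the tail of the look-back.

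The cohort is meant to supply natural-history rates for planning later trials. Surgery between two visits can change acuity or measured sensitivity in one step, and a straight line through few points reads that step as a change in rate. Exposure in a drug trial during the look-back can enter the rate in the same way. Section 7.2 fits a line to each person's points and names age, severity at first visit and vitamin A use as correlates. The SAP replaces this with a mixed model with random intercept and slope. Neither names a term for surgery or trial participation.

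**Working it through.** The plan states no figure for this point, so there is nothing to reproduce. The check is how much of the look-back each window covers.

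**Inputs.** Surgery window 90 days and drug-trial window 6 months (3.4.4); look-back L of 24 to 60 months (3.7.2.1); 1 month = 30.44 days.

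**Surgery.** If baseline is visit -1, coverage = (90 / 30.44) / L = 2.96 / L. If baseline is the first record visit, the 90 days end where the look-back starts and coverage is zero.

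| Baseline taken as | L = 24 months | L = 60 months |
|---|---|---|
| Visit -1 (Section 3) | 2.96/24 = 12.3%; 21.0 months open | 2.96/60 = 4.9%; 57.0 months open |
| First record visit (SAP) | 0%; 24 months open | 0%; 60 months open |

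**Drug trials not aimed at STGD.** A trial still running at enrollment is excluded whenever it began. For a completed trial the end date decides. If enrollment falls g months after visit -1, coverage = max(0, 6 − g) / L. The documents do not give g. With g = 0:

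- L = 24: 6/24 = 25%, leaving 18 months open.
- L = 60: 6/60 = 10%, leaving 54 months open.

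These are upper limits; with g of 6 months or more, coverage is zero.

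**How a step enters a slope.** With two visits T years apart, the fitted slope is (last − first) / T, so a one-time change S adds S / T. With three equally spaced visits the middle one has zero weight and the result is the same. If a share p of eyes is affected in the same direction, the mean slope moves by p × S / T.

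The documents give neither p nor S. As an illustration for acuity only, assume p = 1–5%, S = 5–15 letters and T = 2–5 years:

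- One affected eye: 5/5 = 1 to 15/2 = 7.5 letters per year.
- Cohort mean: 0.01 × 5/5 = 0.01 to 0.05 × 15/2 = 0.375 letters per year.

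The upper cohort figure needs every assumption at its extreme. Under the SAP's mixed model with uneven visits the weights differ, so these figures are approximate.

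**Would the records show it?** PROGSTAR-02 Table 3.6.2 collects interim changes in history at every visit. PROGSTAR-01 Table 3.6.2 has no such row, and the history list in its Section 3.7 names only demographics, vitamin A and mutations. Section 3.7.1.3 does ask for anterior-segment status and cataract grade, which may reveal surgery, but no rule acts on it.

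**Treatment for STGD.** Interventional studies are covered in full: criterion 3 has no time limit and Section 5 runs to the end of the observation period. For therapy outside a study, Section 5 names six months before the observation period. That can mean a window that closes when the period opens, or a prohibition that begins six months earlier and continues through it. The text does not settle which.

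**The case against.** The best defense is that on the SAP reading criterion 2 does what it does in PROGSTAR-02: it clears the 90 days before follow-up starts, and PROGSTAR-02 sets no rule for surgery during follow-up either. That is fair for surgery. It does not help the drug-trial window, which is tied to enrollment. It also rests on an SAP phrase about where characteristics are summarized, not on an eligibility definition, and PROGSTAR-02 at least records interim history at each visit.

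There are partial safeguards: exclusion of confounding ocular disease, the investigator's right to declare a patient ineligible, the image and test quality criterion, central reading, and review of unusual values before slopes are fitted. They may catch some affected eyes. They are matters of judgment, none sets a rule for the observation period, and sites may apply them differently.

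The evidence on size is thin. The letters-per-year figures rest on assumed values and concern a secondary outcome. For the primary outcome, lesion growth or development on autofluorescence, the only route suggested is image quality, and nothing in the documents allows it to be quantified. That objection stands.

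A reader might infer that treatment for STGD inside the look-back is broadly allowed. The documents do not support that, given the open-ended bar on interventional studies. A reader might also see a conflict over a patient who entered such a study after the last used visit, since Section 5 stops at the end of the observation period. This is weak: Section 5 points back to the exclusion criteria, and a patient who meets any one of them is out.

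**Conclusion.** The concern holds in a limited form. As written, 3.4.4 does not exclude intraocular surgery in roughly 88–95% of the look-back if baseline is visit -1, or in any of it if baseline is the first record visit. It does not exclude drug trials unrelated to STGD that ended in at least the earliest 75–90% of the look-back; those percentages assume enrollment coincides with visit -1 and rise if it is later.

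It would go too far to say that the baseline visit lies at the end of the look-back. Section 3 only permits this, for patients screened for PROGSTAR-02, and the SAP points to the start. The surgery gap exists on both readings, and the disagreement itself needs settling. It would also go too far to say that the primary rate is biased, since no effect on it has been shown.

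The weight is minor to moderate. PROGSTAR-02 is unaffected, and the SAP estimates the two cohorts' rates separately. Confidence is high on what the wording leaves open and low on how often it matters.

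**What to change.** 1. Define the baseline visit once for PROGSTAR-01, as the first used visit, in line with the SAP.
2. Keep the 90-day and six-month lengths but anchor them to the observation period: no intraocular surgery from 90 days before the first used visit through visit -1, and no drug-trial participation from six months before the first used visit through visit -1.
3. Where a record is interrupted but a clean run of at least 24 months with two or more visits remains, use only that run instead of excluding the patient. State at which visit the lesion criteria are then checked.
4. Apply the surgery criterion to each included eye. Criterion 2 refers to a primary study eye, but Table 3.4.3-1 designates none and allows both eyes.
5. Reconcile the wording of Section 5 with 3.4.4, so that it is clear what applies to non-study STGD therapy during the observation period.

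The cost is protocol wording and a check of dates in the charts. Surgery dates should often be traceable. Dates of unrelated drug trials may not be; even vitamin A use is recorded only where available, so the plan should say how an unknown history is handled. A few eyes will lose visits or drop out.

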3.5 Primary and Secondary Outcome Variables

The primary outcome variable for the ProgSTAR study is the yearly rate of progression of STGD as reflected by the growth or the development of atrophic lesions measured by FAF imaging.

The secondary outcome variables are:

- Yearly rate of progression of STGD using spectral-domain optical coherence tomography (sd-OCT) to measure the rates of retinal thinning and the loss of photoreceptors.
- Yearly rate of loss of retinal sensitivity as measured by microperimetry.
- Yearly change in best corrected visual acuity (VA).
- Correlation of the presence and/or progression of morphological abnormalities in FAF and sd-OCT images with visual function as measured by microperimetry and BCVA.
- Exploratory analysis to examine factors associated with disease progression, such as participant's use of vitamin A supplementation and mutations in the *ABCA4* gene.

3.6 Measures to Minimize/Avoid Bias

Data from all sites will be sent, using a standardized, de-identified electronic clinical report form (eCRF), to a central data management center at the Dana Center for Preventive Ophthalmology, Wilmer Eye Institute, The Johns Hopkins University School of Medicine, except in the case of data from retinal imaging procedures and microperimetry, which will be sent to a central reading center at the Doheny Eye Institute, Keck School of Medicine, University of Southern California for further processing. Each center shall have undertaken standardized collection of all data. Ophthalmic outcome data from the microperimetry, sd-OCT and fundus autofluorescence assessments will be electronically submitted from the site to the appropriate reading center via secure data upload through the reading center internet website.

Once processed and analyzed by the appropriate reading center, all data will be transferred electronically from the reading center to the Dana Center system via a secure transfer process. Only coded identifiers will be used to identify participants.

3.6.1 Blinding

Not applicable.

3.6.2 Study Data

Table 3.6.2 Study Data				
ASSESSMENT/DATA COLLECTION POINTS	VISIT -4 (if applicable)	VISIT -3 (if applicable)	VISIT -2	Visit -1 (if Patient has Screening Visit of FFBCRI-PROGSTAR 02)
(Best-corrected) visual acuity data	X	X	X	X
Ophthalmic fundus exam data	X	X	X	X
Autofluorescence imaging data and/or	X	X	X	X
Microperimetry data and/or	X	X	X	X
sd-OCT data	X	X	X	X
Vitamin A supplementation data recorded if available	X	X	X	X

See also Fig. 5 where it is explained that there will be two to four datasets (“visits”) per patient.

3.7 Data collection

The Screening consists of review of existing data obtained through the following procedures:

Medical and ophthalmic history:

1. Recording and documentation of demographic information
2. Recording and documentation of vitamin A supplement use
3. Recording and documentation of genetic mutations in the *ABCA4* gene

Description of Standard of Care examinations and procedures the investigators had utilized to obtain data that had been collected for this study include:

Best-corrected Visual acuity (VA):

Visual acuity was measured at a distance of one or four meters using an ETDRS chart. Patients were encouraged to read each letter, and instructed to guess if unsure.

Fundus-Autofluorescence (FAF) and spectral-domain optical coherence tomography (sd-OCT):

Images of patient's eyes were recorded using sd-OCT, and scanning laser ophthalmoscopy (cSLO) in order to acquire fundus autofluorescence images. The computer driven cameras used in these techniques used a beam of light to take images.

Microperimetry:

Patients had undergone an examination of the retinal central visual field using microperimetry. During this procedure patients had to press a button when they saw a little light spot on a screen of a special computer monitor.

An ophthalmic examination will be used to determine if the participant exhibits the typical clinical appearance of STGD in assessing eligibility for the study.

In order to participate in the study, all patients must have documentation of two (2) pathogenic mutations confirmed in the *ABCA4* gene from previously completed genetic testing. If only one *ABCA4* allele contains a pathogenic mutation(s), the patient should have a typical Stargardt phenotype, namely at least one eye must have flecks at the level of the retinal pigment epithelium typical for STGD. The genetic testing will have been previously completed and outside the scope of this study.

The data from the visits will be utilized in the study even if the order of the examinations change from visit to visit or between the practices of the different investigators, and the examinations are performed on different days as long as all measurements were completed within a time window of \pm five (5) weeks of each other.

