3.7.1.3. Evaluations

A member of the study group participating in the study will document all significant observations. At a minimum, this documentation will contain:

- The informed consent process, including any revised consents
- The date of the visit and evidence that the required measurements were performed within 5 weeks of each other
- The genetic information at time of enrollment
- Whether the patient with one affected allele presents with typical Stargardt disease the basis for that conclusion
- Any comments made by the participant about the study, including any significant medical findings
- Any Vitamin A supplement use if available
- A general reference to the provided procedures
- The signature (or initials) and date of all clinicians who made an entry in the progress notes
- The evaluation of (best-corrected) visual acuity
- The evaluation of microperimetry test and recording of mean sensitivity and/or
- The evaluation of spectral-domain optical coherence tomography (sd-OCT) and/or
- The evaluation of fundus autofluorescence
- A summary of the ophthalmologic exam including status of the anterior segment of the eyes, including the cornea, anterior chamber, iris and grading cataract, and dilated fundus exam

In addition, any contact with the participant via telephone or other means that provides significant clinical information will also be documented as described above. Information from the study progress notes and other source documents will be promptly transcribed to eCRFs for transmission to the Coordinating Center. Any changes to information in the study progress notes, other source documents, and CRFs will be properly tracked.

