7.2. Statistical Analyses

Estimating **the yearly growth in the area of the atrophic lesion** as measured by fundus auto-fluorescence:

First exploratory analysis looking at the overall distribution of the outcome at all visits will be carried out, outliers and inconsistent measures will be identified and reviewed. By design, the interval between visits will be variable. For each individual, a slope will be estimated using the available data points by fitting a regression line to the data points. For example, if the i^{th} subject contributes with 3 visits the times $t_{i0}, t_{i,-1}, t_{i,-2}$ with outcome observations $y_{i0}, y_{i,-1}, y_{i,-2}$ will be used to estimate the slope b_i , which will be obtained from the regression $y_{ik}=a+b_i t_{ik}$. ($k=0,-1,-2$). Once the data from each individual has been used to estimate the slope (b), the second stage of the analysis will be to explore which exposures/risk factors determine the heterogeneity of the slopes. Using the slope as the outcome, multivariate regression models will be constructed to identify factors correlating

with progression. Specifically, the correlation to progression of age, severity at first visit, and use of vitamin A supplementation will be examined.

A similar approach to will be used to examine progression over time for the secondary outcomes: retinal thinning, loss of photoreceptors, loss of retinal sensitivity, and changes of BCVA.

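### PROGSTAR-01 ties use of a visit's data to all its tests lying within five weeks of each other, so, read literally, a late secondary test can exclude a usable FAF image from the primary growth rate

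*Protocol*

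**What the plan says.** All section numbers are those of the PROGSTAR-01 (retrospective) protocol unless stated.

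- **3.7 Data collection.** Tests may be in any order and on different days, and the visit's data are still used, "as long as all measurements were completed within a time window of" plus or minus five weeks of each other. There is no exception for FAF.
- **3.7.1.3 Evaluations.** Sites must document "evidence that the required measurements were performed within 5 weeks of each other". This says *required* where 3.7 says *all*, and 5 weeks where 3.7 says plus or minus 5.
- **3.4.3, criterion 5.** "Patients have been followed for at least two (2) visits over a period of at least 24 months", up to 60 months, and the patient "had at least two examinations (same at all visits out of" FAF, sd-OCT and microperimetry).
- **3.6.2, Table 3.6.2.** The three modalities are joined as alternatives (the FAF row reads "Autofluorescence imaging data and/or"), with two to four datasets per patient.
- **7.2 Statistical Analyses.** A regression line is fitted to each patient's available points. "By design, the interval between visits will be variable".
- **7.5.** The main outcome must be present at every eligible visit, so no missing outcome data are expected.
- **SAP.** Progression rates for each testing modality "are estimated and reported separately", using a linear mixed model with a random intercept and a random slope for time. The SAP does not mention the five-week window.

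**The concern.** PROGSTAR-01 has no scheduled visit dates, so this is not a visit window in the usual sense. It measures the distance between different tests. That distance matters when structure is paired with function at one time point. It carries no information about FAF growth, which is a change in one measurement over that measurement's own dates.

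Applied as written, the condition lets the timing of a secondary test decide whether a primary-outcome observation counts. The data are routine-care records that cannot be collected again, the disease is rare, and two visits over 24 months is the floor. Losing one FAF point can therefore cost precision and, in some patients, the whole growth rate.

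**Working it through.** **1. What each analysis needs.** The growth slope in 7.2 needs pairs of FAF area and time, at any spacing. The SAP's mixed model needs the same. The structure-function correlation, and the use of secondary variables to study lesion development (section 3, Figure 6, Scenarios 2 and 3), need different tests at about the same time. Only this second group needs a limit on the gap between tests.

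**2. The plan's own sample size.** Inputs from 7.1: difference 0.2 mm² per year, SD 0.9, two-sided alpha 0.05, power 80%, Wilcoxon test.

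n = [0.9 × (1.960 + 0.842) / 0.2]² = 159. Multiplying by π/3 for the Wilcoxon test gives 167 (169 using the noncentral t). The stated 170 reproduces, with power 0.80 to 0.81. The plan's arithmetic is not in question.

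**3. Patient loss by visit count.** Let q be the share of visits with a test outside the window. The documents give no value, so q is assumed, with failures independent between visits. A patient is lost when fewer than two visits remain:

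- two visits: 1 − (1 − q)²
- three visits: q³ + 3q²(1 − q)
- four visits: q⁴ + 4q³(1 − q)

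| Assumed q | Two visits | Three visits | Four visits |
|---|---|---|---|
| 5% | 9.8% | 0.7% | 0.05% |
| 10% | 19% | 2.8% | 0.4% |
| 20% | 36% | 10.4% | 2.7% |

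If failures clustered completely within patients instead, the loss would be q whatever the number of visits (10% at q = 10%).

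**4. The 24-month span.** A patient seen at 0, 12 and 24 months who loses either end visit keeps a 12-month span and no longer meets criterion 5. Both end visits are needed, so the loss is again 1 − (1 − q)², or 19% at q = 10% rather than 2.8%.

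**5. What this could do to power.** Power = Φ[0.2 × √(n × 3/π) / 0.9 − 1.96], at q = 10%:

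- 170 patients, all with two visits: n = 170 × 0.81 = 138, power 0.72
- 170 patients, all with three visits, no span loss: n = 170 × 0.972 = 165, power 0.80
- 250 patients, all with two visits: n = 250 × 0.81 = 202, power 0.87

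The result depends almost entirely on quantities that the documents do not give.

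**6. Precision for patients who stay in.** For visits at 0, 20, 40 and 60 months, the sum of squares of time is 2000/144 = 13.89 yr². Without the last visit it is 800/144 = 5.56, so the measurement-error variance of the slope rises by a factor of 2.5. Without an interior visit it is 12.96, a factor of 1.07. The cost lies mainly in end visits.

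**The case against.** The strongest reply is that no section says an FAF image is thrown away. Section 3.7 is permissive in tone, and it does not say whether an out-of-window test leads to dropping that test, dropping the visit or recording a deviation. This stands as far as it goes: exclusion is the literal consequence of a condition of use, not an explicit instruction. If the handling is instead undefined, the same sentence is needed to define it.

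Second, 3.7.1.3 limits the window to required measurements, and Table 3.6.2 treats the modalities as alternatives, so a late optional third modality need not void a visit. This also stands, but 3.7 says all, and even the narrower wording lets a late required second modality exclude the visit.

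Third, the window has a purpose. Structure-function correlation is a stated objective, and for Figure 6 Scenarios 2 and 3 the other modalities serve the development part of the primary outcome. If one visit date serves all tests, the window also limits timing error: 3.7.1.3 records a visit date, and 7.2 does not say that its time variable is the FAF date. Five weeks is about 4.8% of 24 months. These are reasons to keep the window for paired analyses. Using each examination's own date removes the timing-error argument for the single-modality rates.

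Fourth, screening here is a review of existing records, so patients who fail would largely never be enrolled, and sites may enrol up to 250. Loss from a fixed 170 is therefore not the right picture. This stands and limits what the power figures can show.

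**Conclusion.** The point holds as a specification problem. Read literally, 3.7 can exclude usable FAF observations from an analysis that needs only FAF area and date. This can remove a two-visit patient, or one whose remaining span falls below 24 months. The size is unknown. The 19%, 2.8% and 0.4% figures rest on an assumed 10% of visits out of window, on independence between visits, and on counting visits alone; three-visit patients with a span of exactly 24 months would lose more.

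A reader might infer more than the documents support:

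- *That whole patients are often lost.* Neither the out-of-window rate nor the mix of two-, three- and four-visit patients is given.
- *That the study drops to 72% power or lower.* That is the case in which all 170 patients have two visits and loss acts as attrition after enrolment. With three visits, or with enrolment towards 250, power stays near or above 80% at q = 10%.
- *That the patients who worsen most are selectively lost.* This is possible, but nothing in the documents shows it.
- *That criterion 5 is also wrong in asking for a second modality at all visits.* Choosing patients who can contribute to the multimodal objectives is a legitimate eligibility trade-off, and lesion development relies on the other modalities.

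**What to change.** In PROGSTAR-01 3.7, and in the SAP, which is silent on the window, state that:

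1. each modality's progression rate uses every gradable examination, with its own acquisition date as the time variable;
2. the five-week window applies only to analyses that pair modalities, namely the structure-function correlation and the use of secondary variables to study lesion development;
3. one definition of the window replaces the two now in 3.7 and 3.7.1.3, settling *all* against *required*, and whether plus or minus five weeks means a maximum spread of 5 or 10 weeks;
4. the number of visits outside the window is reported.

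Leave criterion 5 unchanged.

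The cost is wording and the use of per-examination dates; no new procedures are needed. The downside is that patient and visit numbers will differ between outcomes, so each table must state its own denominator. That fits the SAP's separate reporting by modality.
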